- 4. Global Rating Scores are overall ratings of the patients' status at the time of rating (on a scale of 0 meaning no drug problem to 100 meaning worst case ever). These ratings are completed at screening and every four weeks thereafter. The patients are also rated on a scale from 1 (much worse) to 5 (much better) as compared to the previous rating. Both types of ratings are completed separately by the staff as well as the patients. The staff will also be asked to rate the patient at termination in comparison to how the patient was at the time of entry into the study using the five-point scale.

Statistical Methods

Analysis of the Incidence of Opiate Abuse

As mentioned earlier, the incidence of opiate abuse will be estimated by the urine samples obtained and analyzed three times a week, i.e., on Mondays, Wednesdays and Fridays. Thus, in this 16-week maintenance study, up to 48 urine samples will be collected for each patient in the study. However, given the experience with the ARC 090 Study which had as high as 80% dropout rate in the low dose methadone group, the dropout rates are likely to be high and even those who stay in the study are likely to miss a substantial number of clinic visits and, thus, there are likely to be a lot of missing urine samples. In the ARC 090 study, on the average, 20% of the urine samples were missing. Consequently, in order to handle missing values and to simplify statistical analysis, a weekly index of urine positivity for opiates has been developed, or in other words, 48 data points will be reduced to 16 weekly data points. For a given patient, his first study week will be days 1-7 in the study, second study week will be days 8-14 in the study, etc.

The following **data reduction** algorithm will be used:

- 1. If there is at least one positive urine during a given study week, that week will be considered positive for opiates (a *positive week*).
- 2. If all three samples during a week are found to be missing, that week will be considered a *positive week*.
- 3. If conditions 1 and 2 above are not met, the week will be considered to be a *negative week*.

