As an alternative to the (parametric) analysis of variance considered above, data for each patient can be scored, e.g., 0 for a negative urine and 1 for a positive urine and the sum of scores for each patient can be calculated. These sum of scores can be ranked and a (non-parametric) analysis of variance for these ranks can be used. However, there are several problems with this approach. Firstly, this approach also does not permit censored observations. It was suggested by [name] of FDA that the missing and censored data points should be scored as 1, i. e., all urine samples for which data are not available be considered positive. Since, based on the dropout rates in ARC 090 study (60% to 80%), we expect a high dropout rate in this study too, this analysis will be based on more unreal, i.e., made up data than the real observed data. This certainly would not be advisable. Secondly, these sum of scores obscure the pattern of positive and negative urines, e.g., a score of 25

does not inform whether these 25 positive urines came from first half of the study or second half of the study. Thirdly, the differences in ranks are not directly interpretable for a clinician. For example, mean rank for a group A may be 22.2 and group B, 28.2, but this difference of 6 in mean ranks is not interpretable in terms of percent positive urines. For these reasons, it was decided that (non-parametric) analysis of variance based on ranks would not be a suitable procedure for the proposed study.

Since each positive urine is considered to be indicative of an episode of drug abuse and as such a possible treatment failure, these data can be analyzed by using one of the multiple failure models proposed in the literature. In this study, 48 urine samples will be collected from each patient and as such, a patient can experience up to 48 failures. Many methods to analyze multiple failures have been proposed but the one based on Cox's proportional hazards model by Wei and others (JASA, 84, 1065-1073, 1989) imposes least restrictive structure on the data and is proposed to be used for this multicenter study. The computer program given in Lin (1990) will be used.

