The reduced data, i.e., 16 data points as explained earlier, one for each week will be used for this analysis. Since, treatment assignment will be the only covariate used, 16 regression coefficients will be estimated. A common regression coefficient estimated as $\hat{a}=\hat{o}c_i\hat{a}_i$ where \hat{a}_i is the regression coefficient for failure i (i=1, ..., 16) will be tested for statistical significance and the common hazard ratio $HR=e^{\hat{a}}$ will be estimated.

The estimate of common \hat{a} (common HR), if found to be statistically significantly different from zero (one) for the data pooled for all study centers for buprenorphine 8 mg versus buprenorphine 1 mg analysis only at \hat{a} =.05, will be indicative of the superiority of one drug over the other for FDA approval purposes.

This model was successfully used to analyze the ARC 090 study using a 17 dimensional model using the same data reduction algorithm as proposed for this study and buprenorphine was found to be statistically significantly better than both methadone 20 mg (p=.015) and methadone 60 mg (p=.037). The common hazard ratio was found to be .746 for the buprenorphine/60 mg methadone comparison and .706 for the buprenorphine/20 mg methadone comparison.

The common hazard ratio estimable from this model has an easy clinically understandable interpretation. For example, a common hazard ratio of .746 for the buprenorphine/60 mg methadone comparison means that the conditional probability of a buprenorphine treated addict, on the average, has a 25.4% less chance of abusing drug (opiate) compared to a methadone 60 mg treated addict provided none of them have yet used opiate. In other words, after the treatment begins, a buprenorphine treated addict has, on the average, 25.4% less chance of using opiate the first time compared to 60 mg methadone treated addict. In addition, the hazards ratios or comparative conditional probabilities for using the opiate the first time, the second time etc. are also estimable from \hat{a}_1 , \hat{a}_2 , etc. The relationship between the first, second positive urines etc. can also be studied by variance-covariance matrix of \hat{a} 's. Consequently, use of this model has the following advantages:

? This model can be used for censored data.

- ? Hazard ratios estimable from this model have easy clinically understandable interpretations.
- ? The relationship (pattern) between various positive urines can be studied.

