The time to first failures, second failures, etc., will be counted from the beginning of the study in days. For example, for the first positive week, if the first positive urine during study week seven was observed on day 45, the time to first failure will be 45 days. For the second positive week if the first positive urine during study week ten was observed on day 66, the time to second failure will be 66 days. If the week was considered positive because all samples during that week were missing, the time to first missing urine during that week will be the time to failure.

The **main** analysis for FDA approval purposes will be done by pooling data from all study centers and by computing â and HR. A subanalysis will be done for each study center to study treatment-center interaction. Subanalyses will also be done on the pooled data for males and females separately.

Common hazard ratios for 8 mg vs. 1 mg, 4 mg vs. 1 mg and 16 mg vs. 1 mg analysis will be plotted and displayed for comparison purposes only. Hazard ratios for each study week for each analysis will also be displayed.

Analysis Primarily for FDA Medical Review

For the analyses specified below, the following data reduction algorithm will be used:

- 1. If two or more urine samples for a given study week are found to be missing for a given patient, that week will be considered to be a missing week for that patient.
- 2. If at least two urine samples were available and analyzed for a given patient during a given week and if at least one urine sample was found to be positive for opiates, that week will be considered to be positive for opiates or a positive week. Otherwise, it will be considered to be a negative week.

The data for the missing weeks will be excluded from the following analyses:

1. Percent positive urines for each study week will be computed and plotted for each treatment group. For the data pooled for the total study period, a z statistic will be calculated and four preplanned *a priori* comparisons will be made between the proportions of positive urines for 1 mg vs. 4, 8 and 16 mg treatments respectively and for 1 mg vs. 4+8+16 mg comparison. Each of these *a priori* comparisons will be considered to be statistically significant at p value of .05 or below. Histograms will be plotted for percent positive urines for each of the four treatment groups for the total study period. No adjustment will be made for multiple comparisons.

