Since each urine sample found to be positive for opiates can be considered to be a treatment failure, up to 51 failures were observable in the 17-week (maintenance) ARC 090 study and up to 48 failures will be observable in the proposed 16-week study. Consequently, the analyses of data from these trials constitute analysis of multiple failures. Many methods to analyze multiple failures have been proposed but the one based on Cox's proportional hazards model by Wei and others (1989) imposes the least restrictive structure on the data and was used to analyze ARC 090 data and is proposed to be used for the multicenter study.

Briefly, this model estimates a regression coefficient between log hazard rate (dependent variable) and the treatment assignment (independent variable) for each failure. Tests of hypotheses to draw inference for each regression coefficient are available. A test of hypothesis to draw inference for a common regression coefficient which is a linear combination of individual regression coefficient is also available. Since the primary interest of the proposed study would be to compare the overall efficacy of the two treatments, the sample size calculations were based on the ability to draw inference for the common regression coefficient.

Since the parameter estimation may be mathematically extremely difficult for a 51- or a 48-dimensional model, the data will be reduced to 16 dimensions by deriving the index of weekly failures described earlier.

In the ARC 090 study, the sample sizes were 53 and 55 for the 8 mg buprenorphine and 20 mg methadone groups, respectively. The estimate of common regression coefficient was found to be 0.348 (p=.015) indicating superiority of buprenorphine over 20 mg methadone treatment. The sample sizes of 120 for each treatment group in the proposed study are more than double of what they were for the ARC 090 study and should provide sufficient cushion against the unexpected. However, the formal sample size/power calculations were still performed using the sample size calculation methods for multiple regression and correlation analyses given in Cohen (1988) using

Table 9.3.2 in this book.

Using Table 9.3.2, the following powers values were obtained for various values of f

f^2	ë	Correlation r	Power
.02	4.8	.14	60%
.15	36.2	.36	99%
.35	84.4	.50	99%

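### The covariance matrix of the 16 treatment coefficients cannot show how one positive urine follows another, though the plan offers it for that purpose

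*Combined protocol and SAP*

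**What the plan says.** All references are to the parent protocol, Statistical Methods, Analysis of the Incidence of Opiate Abuse, unless noted.

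- The three urines per week are condensed: "48 data points will be reduced to 16 weekly data points". The rule is "If there is at least one positive urine during a given study week, that week will be considered positive for opiates"; a week with all three samples missing is also counted positive.
- The main model is the marginal Cox model for multiple failures. In it, "treatment assignment will be the only covariate used, 16 regression coefficients will be estimated", one for each successive positive week.
- On the time scale, "The time to first failures, second failures, etc., will be counted from the beginning of the study in" days.
- On pattern, "The relationship between the first, second positive urines etc. can also be studied by variance-covariance matrix of" the coefficients. The list of three advantages then includes "The relationship (pattern) between various positive urines can be studied".
- The rank analysis is rejected partly because "these sum of scores obscure the pattern of positive and negative urines". The example given is whether 25 positives fell in the first or the second half of the study.

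**The concern.** Each coefficient is a treatment effect on the time to the k-th positive week. The covariance of two of them says how their estimation errors move together. Because the k-th failure time is contained in the (k+1)-th, those errors are tied whatever patients do from week to week.

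A reader who took the plan at its word would see correlations of .6 to .9 between neighbouring coefficients and could conclude that one positive urine leads to the next. The same figures appear when the weeks are independent. At stake is a descriptive statement about pattern of use in data meant to support an NDA, and one of the stated reasons for preferring this model. The efficacy decision is not at stake.

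**Working it through.** **Inputs from the plan.** Sixteen weekly indices, treatment as the only covariate, times from study start, and 120 patients per arm ("The sample sizes of 120 for each treatment group in the proposed study are more than double" those of the earlier study, Sample Size Consideration). **Assumptions.** The documents give no weekly positive rate and no week-to-week dependence. Rates of .3, .5 and .7 and a range of dependence were therefore tried.

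**The plan's own figures.** It gives none for the covariance matrix. The neighbouring common coefficient reproduces: exp(−0.348) = .706, the stated hazard ratio. It does not bear on this point.

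**Step 1: ordering alone.** Write the k-th failure time as T_k = G_1 + … + G_k, where the G are gaps between positive weeks. If the gaps are independent with equal variance, then for k < l corr(T_k, T_l) = k/√(kl) = √(k/l). This gives √(1/2) = .71 for failures 1–2, √(2/3) = .82 for 2–3 and √(3/4) = .87 for 3–4. In a first-order chain the gaps after the first positive are independent and identically distributed whether use alternates, persists or is unrelated. Only the first wait depends on the starting state.

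**Step 2: closed form at a 50% weekly rate.** Let a be the probability of switching state between weeks. A gap equals 1 with probability 1 − a, and otherwise 1 plus a geometric wait with parameter a.

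- Variance of later gaps: V = (2 − a)/a − 1 = (2 − 2a)/a.
- Variance of the first wait from a random state: V1 = (2 − a)/(2a²) − 1/(4a²) = (3 − 2a)/(4a²). From a positive start, V1 = V.
- corr(T_1, T_2) = √[V1/(V1 + V)], before end-of-study censoring.

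**Step 3: simulation of the planned model.** 240 patients, no dropout, no treatment effect. Ranges cover separate simulation runs. P(+ after +) and P(+ after −) are shown in the first column.

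| Pattern | a | V1 | V | corr(T_1, T_2) | Simulated correlation, coefficients 1–2 |
|---|---|---|---|---|---|
| Unrelated, .50/.50 | .50 | 2.00 | 2.00 | .71 | .64–.68 |
| Alternating, .30/.70 | .70 | .816 | .857 | .70 | .67 |
| Alternating, .25/.75 | .75 | .667 | .667 | .71 | .65 |
| Alternating, .20/.80 | .80 | .547 | .500 | .72 | .68 |
| Persistent, .80/.20, random start | .20 | 16.25 | 8.00 | .82 | .79–.83 |
| Persistent, .80/.20, positive start | .20 | 8.00 | 8.00 | .71 | .58–.65 |

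For coefficients 3–4 the simulated value was .86 with unrelated weeks and .84 with alternating weeks. The sampling SD of one entry in a trial of 240 is about .04 to .07.

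**Step 4: dropout and other rates.** Dropout of 0, 30% and 70% was treated as censoring, with rates .3 to .7 and lag-1 correlation −.4 to −.6. Over all estimable pairs, alternating and unrelated use differed by .006 to .037 on average, against a sampling SD of .036 to .058.

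**Step 5: opposite patterns, same entry.** At a weekly rate of .7 the 1–2 entry does move, from .63–.66 with unrelated weeks. For dropout of 0, 30% and 70%, moderately alternating use gave .58, .54 and .56. Persistent use from a positive start gave .59, .58 and .52.

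**Step 6: stable differences between patients.** Giving each patient a fixed personal rate, with no week-to-week dependence, raised the 1–2 entry from .67 to .85 at a 50% rate without dropout. Persistence from a random start raised it from .67 to .81.

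**The case against.** **The sentence is a remark within a rationale.** The plan says the relationship can be studied this way. It schedules no table, test or interpretation of the matrix. The outputs named are common hazard ratios and hazard ratios by study week. This stands, so a reader should not infer that the trial is committed to reporting spurious relationships.

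**The plan's own example of pattern is timing.** Early versus late positives are addressed by the failure-specific hazard ratios, the weekly percent-positive plots, the results at each testing opportunity (Analysis Primarily for FDA Medical Review) and the urine profiles of all patients (Exploratory Analyses to Identify Subgroups). This also stands. The third advantage need not go altogether, and urine-level sequence is absent only from the main model.

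**The matrix carries some information.** From a random start, persistence moves the 1–2 entry by .81 − .67 = .14, which is .14/.07 = 2 to .14/.04 = 3.5 sampling SDs. Strict alternation also changes the matrix. It would be wrong to say that nothing registers. But entrants must have used daily for the past month (Inclusion Criteria), so a positive start is a relevant case, and there the shift disappears or reverses. Where the entry does rise, stable patient differences explain it equally well.

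**The simulation is not this trial.** No weekly rate is documented, and the rule counting all-missing weeks as positive was not simulated. This is fair for the exact values. The ordering argument in Step 1 does not depend on the weekly rate.

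**Conclusion.** The concern holds as a fault in interpretation. The matrix is strongly positive by ordering alone. It does not separate unrelated from moderately alternating use, and its response to persistence depends on the starting state and is confounded with stable differences between patients. It should not be cited as evidence of how one positive follows another.

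The size is small. A reader might infer that the main test is compromised; the documents do not support that. The robust covariance is what the common-coefficient test needs, and the 8 mg versus 1 mg comparison and its sample size are unchanged.

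The numerical results rest on assumed weekly rates of .3 to .7, first-order dependence and dropout treated as censoring. Moderate alternation means a lag-1 correlation of about −.4 to −.6. Under stronger alternation the similarity weakens: at −.8 the 1–2 entry ranged from .57 to .69.

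**What to change.** Delete the covariance-matrix sentence. Reword the third advantage so that it claims only timing, through the failure-specific hazard ratios.

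If the week-to-week relationship is of interest, describe it directly by arm: the proportion positive in week t+1 after a positive week and after a negative week, with patient-clustered errors. Use only pairs of weeks in which both have observed urines. Exclude all-missing and post-dropout weeks.

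That exclusion matters. The plan does not say whether weeks after dropout count as all-missing. Suppose they were scored positive, with independent 50% weeks and the last observed week uniform on 1 to 15 (mean 8). A completer contributes on average 7.5 positive starts (3.75 followed by a positive) and 7.5 negative starts (3.75). A dropout contributes 11 (9.25) and 4 (2.25).

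- 30% dropout: after a positive, (.7×3.75 + .3×9.25)/(.7×7.5 + .3×11) = 5.40/8.55 = .63. After a negative, 3.30/6.45 = .51.
- 70% dropout: 7.60/9.95 = .76 after a positive, and 2.70/5.05 = .53 after a negative.

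That would be apparent persistence where there is none.

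The cost is two wording changes and, if wanted, one small descriptive analysis on data already collected. Its limitation is that it is conditional on attendance, which should be stated beside the result.
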